## **Subject Enrollment**

### Phone Screen

#### *Information about the study:*

Potential subjects will be briefly informed about the study. We will explain that the purpose of the research is to identify factors that can help to promote cognitive and brain health in older adults. This will be accomplished through examining the impact of different training programs involving physical or cognitive exercises and activities. Potential subjects will be told that there are 4 different training programs: two programs involve cognitive training, one involves training in mindfulness (awareness), and one involves physical training. We will make it clear that participants do not get to choose the program, but will be assigned by chance (randomized) to one of these training interventions. All participants will come to Brigham and Women's hospital for a baseline assessment and for a post-intervention assessment, which will be the same regardless of the training program in which a subject participates. These assessments will include cognitive, brain wave, and biological measures of brain function and adaptation. Training will take place in the participant's own home over a 5 week period. They will be paid for their time and the cost of parking at BWH will be covered.

#### *Information about the potential subject:*

All potential subjects will be screened by phone, using a standardized telephone interview that reviews neurological, medical, and psychiatric conditions, and conducts a brief cognitive test.

Eligible subjects interested in participating will be asked to assent to being randomized to one of the four training programs, which will be recorded on the phone screen in-take form.

### Permission to Contact a Potential Subject's PCP

Eligible subjects will be informed that one of the interventions is a physical exercise training program that involves a mild to moderate degree of exertion. All subjects will need "permission" from their PCPs indicating they can safely participate in physical exercise.

Potential subjects who remain eligible and interested after the phone screen will be mailed a form to sign that will be sent to their PCP authorizing them to complete it. The form will include a brief description of the physical exercise program and ask the PCP to state whether or not it is medically safe for the person to participate in such a training program, if he/she were assigned to it. We will include a stamped, addressed envelope for subjects to mail the form back to us in.

After we receive written authorization from the potential subject, we will contact the PCP's office, fax the form, and provide our secure fax number where the completed form should be sent back. After receiving the completed form from the PCP, we will contact the potential subject to let her/him know if she/he is eligible to participate. If eligible, we will schedule the pre-intervention assessment, where informed consent will be obtained and additional screening procedures and baseline testing will take place (see below).

### Randomization

## Detailed Protocol: SAGE

Subjects will be randomly assigned to one of 4 conditions (3 experimental, 1 active control), which will be determined prior to the first visit so that the appropriate informed consent form can be completed:

1. Cognitive training using Cogmed (Pearson®)
2. Awareness (“mindfulness”) training
3. Physical exercise training using an interactive video platform
4. Active control condition using the non-adaptive Cogmed program

We plan to continue to recruit subjects until all 4 arms of the protocol are filled.

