## Detailed Protocol: SAGE

Subjects will be recruited at the two sites with the aim of obtaining a representative sample of healthy, elderly participants 65 and older in each country. At BWH, subjects will be recruited through several channels, including announcements in local newspapers and other available media; outreach to independent living communities; senior activity centers and organizations; and through existing databases for studies of healthy aging that exist at BWH.

To be included in the study, participants must:

1. Be 65 or older
2. Have  $\geq 8$  years of education
3. Be sufficiently fluent in the English language to understand instructions and perform the neuropsychological tests (as the purpose of the project is to study healthy aging)
4. Score above levels indicating possible cognitive impairment on the Mini Mental State Exam (MMSE) ( $\geq 26$ ) [87]
5. Have an estimated intelligence quotient (IQ) score  $\geq 90$  based on the American National Reading Test (AmNART) [88]
6. Have a score within 2 SD of the age-appropriate mean on the short form of the Boston Naming Test [89, 90]
7. Have a score within 2 SD of the age-appropriate mean on the Logical Memory Subtest of the Wechsler Memory Scale—Third Edition [91]

Subjects will be excluded for any of the following reasons:

1. History of CNS diseases or major psychiatric disorders based on DSM-IV criteria [92]
2. Score of  $> 10$  on the Geriatric Depression Scale [93]
3. Corrected visual acuity worse than 20-50 as tested by a Snellen wall chart
4. Severe hearing disability that would interfere with their ability to participate in the experiments (e.g., to hear instructions and participate in cognitive testing)
5. Medical conditions (e.g., heart or pulmonary disease) that would prevent them from participating in the physical exercise training program
6. Evidence of substantial functional decline based on interview questions and completion of a questionnaire based on the Clinical Dementia Rating Scale [94] by an informant who knows the subject well

Permission will be obtained from subjects to contact their primary care physicians (PCPs). PCPs will be asked to confirm that if their patient were assigned to the physical training condition, he/she could safely participate. Subjects will be excluded if their PCP does not confirm that they can safely participate.

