## Study Procedures

### Pre-Intervention Assessment

The initial screening evaluation will take place over two half-day sessions, each lasting 3 to 3.5 hours in a designated room in the Laboratory of Healthy Cognitive Aging, Center for Brain/Mind Medicine, BWH, [name].

The sessions can be completed over one or two days, depending on the subject’s preference.

### Pre-Intervention Assessment Session 1

The first session will include completion of informed consent, a medical history, demographic information, including socioeconomic status (SES), survey questionnaires, and tests of visual acuity.

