### Screening Evaluation (for inclusion/exclusion)

#### Cognitive Screen

- *The Mini-Mental State Examination (MMSE)*, a broad cognitive test on memory, spatial ability, memory and orientation, commonly used to screen for cognitive impairment [87]
- *American National Adult Reading Test (AmNART)*, a test of word pronunciation that provides an estimated IQ [88]
- Logical Memory I and II, Wechsler Memory Scale—Third Edition, a test of verbal memory [91]
- *Boston Naming Test (Short-form, 15-items)*, a test of confrontation naming [89, 90].

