## Detailed Protocol: SAGE

1. Single task (walking at a comfortable pace)
2. Dual task (walking at a comfortable pace while simultaneously counting backwards by 3's, beginning with a 3 digit number told to the subject)

Every trial involving serial 3's will start from a different three digit number to reduce learning effects. Subjects will be given an opportunity to carry out an untimed practice trial. Under the dual task condition, subjects will be instructed to perform as well as they can on both tasks (i.e., no specified prioritization). Each condition will be done 2 times, with the order counterbalanced across subjects. The first and last meter (gait start up and slow down) will not be counted in the measurements. Time to walk 8 meters and number of steps taken will be measured. Under the dual task, we will also track how many numbers are generated while carrying out the serial 3's task (both correct and incorrect responses). In addition, the single task of counting backwards by 3's for 20 seconds will be tested twice in a seated position (once prior to and once after the gait testing).

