### Informant Questionnaire

Subjects will select someone who knows them well (family member or friend) to complete a set of questionnaires. One questionnaire will provide information about a person's level of functioning (based on the Clinical Dementia Rating Scale [94]), and another will inquire about a person's level of engagement (Apathy Scale [95]). The questionnaires will be enclosed with a letter explaining how to complete the forms. We will provide a stamped, addressed envelope to return the questionnaires to us. A backup plan will be to mail these materials directly to the informant selected. This would occur if the materials were misplaced or if the subject requests us to do so. Informants will be compensated for their time by a \$10 check that will be mailed to them.

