### Outcome Measures (Dependent variables measured at baseline and after the 5 week intervention)

- *Cambridge Neuropsychological Test Automated Battery (CANTAB)*, a computerized assessment of cognitive functions:
  - CANTAB Paired Associate Learning (PAL) – assesses visual memory and new learning
  - CANTAB Attention Switching Task (AST) – measures cued attentional set-shifting
  - CANTAB Reaction Time (RTI) – measures speed of response to visual target when the stimulus is either predictable (simple RT) or unpredictable (choice RT)
  - CANTAB Spatial Span (SSP) – assesses working memory
  - CANTAB One Touch Stockings of Cambridge (OTS) – a test of non-verbal reasoning
- *Trail Making Test, Parts A and B*, tests of visual attention and task switching [96]
- *Digit Symbol Coding, WAIS-IV*, a test of processing speed [96]
- *Controlled Oral Word Association Test (COWAT)*, a test of verbal retrieval and word generation [97]
- *Categorical Fluency* (a test of rapid retrieval of semantic knowledge) [97]

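### The arm is fixed, and an arm-specific consent form chosen, before consent, eligibility and baseline are complete, so refusal and entry can depend on the type of training

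*Protocol*

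**What the plan says.** Under Subject Enrollment, Randomization, the protocol assigns subjects to one of four conditions and says of the assignment: "which will be determined prior to the first visit so that the appropriate informed consent form can be completed". The stated purpose makes the form depend on the arm.

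The later steps are placed as follows.

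- **Consent.** The section on contacting the PCP describes the pre-intervention assessment as the occasion "where informed consent will be obtained and additional screening procedures and baseline testing will take place". Session 1 confirms it: "The first session will include completion of informed consent, a medical history, demographic information".
- **Eligibility in person.** The screening evaluation in Session 1 holds the cognitive and depression screens, visual acuity and a structured neurological examination.
- **Eligibility by informant.** Exclusion criterion 6 under Subject Selection is "Evidence of substantial functional decline based on interview questions and completion of a questionnaire", the questionnaire being filled in by someone who knows the subject. It is handed out for return by post: "We will provide a stamped, addressed envelope to return the questionnaires to us". No return deadline is given.
- **Baselines.** Gait is measured in the same assessment. The cognitive tests are headed as "Dependent variables measured at baseline and after the 5 week intervention". Blood, ERP and TCD follow in Session 2.

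Before the first visit there are a phone screen, in which subjects hear of all four programs and assent to being randomized, and PCP clearance for exercise, which is required whatever the arm. The protocol nowhere says that the assignment is concealed from subjects, enrolling staff or testers while consent, screening and baseline take place.

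**The concern.** Randomization protects a comparison when nobody's entry can depend on the arm drawn. Here the arm exists, and has already determined a document that the subject reads, before the subject has consented and before eligibility is confirmed. Someone content to be randomized in the abstract may decline on learning that the draw is five weeks of exercise, or of mindfulness. A staff member who knows the arm may weigh a borderline history differently. If either happens at different rates across training types, the groups analysed are no longer the groups randomized.

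Two features could make such a loss hard to see. Recruitment continues until all four arms are filled, and the target of 200 counts completers. The protocol does not say whether people lost after assignment are replaced. If they are, equal final arm sizes would not reveal an arm-related loss.

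There is a further weakness at baseline. Outcome baselines are also taken after the arm can be known, and some depend on effort. In the dual-task gait test, for example, "subjects will be instructed to perform as well as they can on both tasks". Biostatistical Analysis makes cognitive change scores the main outcome and names baseline cognition as a covariate, so the baseline enters the analysis twice.

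**Working it through.** **1. Order of events.** Put in sequence, the protocol gives: phone screen and assent to randomization; PCP clearance; arm determined and form chosen; first visit with consent, medical history and in-person screening; outcome baselines in Sessions 1 and 2; a week of accelerometry; home introduction visit. Consent, final eligibility and all outcome baselines fall after the arm is fixed. An analysis plan does not set this order; the protocol does.

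**2. Which eligibility checks follow assignment.** Some are numeric and leave little room for discretion: MMSE, AmNART, Boston Naming, Logical Memory, depression score and visual acuity. Others need judgement: functional decline, from interview and informant; and the medical history and neurological examination, which bear on the exclusion for CNS disease. Selective screening is thus possible but secondary to refusal.

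**3. Size of a refusal effect.** The protocol states no figure to reproduce: no alpha, power, SD, allocation ratio or refusal rate. What follows is illustration on assumed inputs.

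- n = 200/4 = 50 per arm. The 200 is stated; equal allocation is assumed.
- A single pairwise two-sided 5% t-test, not the planned MANCOVA.
- One arm alone loses a fraction p = 0.10 to 0.20 at consent; the comparison arm loses none.
- Motivation correlates r = 0.2 to 0.5 with change.
- The tendency to refuse correlates λ with motivation. λ = 1 means exactly the least motivated refuse; λ = 0.5 means motivation drives refusal in part.

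Removing the lowest fraction p of a standard normal refusal score raises the mean of the remainder by φ(z_p)/(1 − p):

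- p = 0.10: 0.1755/0.90 = 0.195
- p = 0.20: 0.2800/0.80 = 0.350

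Bias in change-score SD = λ × r × φ(z_p)/(1 − p). The standard error of a difference, in the same unit, is √(2/50) = 0.20. The false-positive rate comes from the noncentral t with 98 degrees of freedom and noncentrality bias/0.20.

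| λ | p | r | Bias (change-score SD) | False positives |
|---|---|---|---|---|
| 0.5 | 0.10 | 0.2 | 0.5 × 0.2 × 0.195 = 0.02 | 5.1% |
| 0.5 | 0.20 | 0.5 | 0.5 × 0.5 × 0.350 = 0.09 | 7.2% |
| 1 | 0.10 | 0.2 | 0.2 × 0.195 = 0.04 | 5.4% |
| 1 | 0.20 | 0.5 | 0.5 × 0.350 = 0.18 | 13.9% |

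The λ = 1 rows are an upper bound for each p and r. If refusal is alike across arms, the bias by this route is zero.

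**4. Effort at baseline.** Bias in a change score equals the post-test effort shift minus the baseline effort shift. Subjects know their training type at post-test under any order of events. If knowing it alters effort equally on both occasions, the two shifts cancel in the change score. If it alters effort only at baseline, they do not. The documents do not say which pattern holds, so no figure is given for this route.

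**The case against.** **Disclosure is inferred.** No section says that subjects or testers are told the arm before baseline, and the consent forms are not in the review copy. This stands in part. A form that must match the arm makes disclosure of training type likely to the subject and to whoever obtains consent; otherwise there would be little reason to assign before the visit. Disclosure to outcome testers is not established.

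**Safeguards exist.** Subjects are told that they cannot choose, they assent by phone to any of the four programs, and every subject needs PCP clearance for exercise. These lower the risk. They all come before the arm is known, however, and accepting a lottery is not the same as accepting its result.

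**Not every contrast or measure is exposed.** The instructions for adaptive and non-adaptive Cogmed are identical, so those two arms may share a form and the contrast between them may be little affected. BDNF does not depend on effort in testing. Both points stand.

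**The sizes are assumed.** This stands. The largest figure needs one arm alone to lose exactly its least motivated 20%. The planned model also adjusts for age and baseline cognition, which the illustration does not.

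**A stronger reading is tempting on effort.** A reader might infer that knowing the arm at baseline biases change scores in a predictable way and that late release would remove the problem. The documents do not support that. If the effort effect persists to post-test, it cancels in change scores under the current order, and late release would leave it at post-test only. The case for the fix therefore rests on entry to the trial, not on a calculated effort effect.

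**Conclusion.** The concern holds as a weakness in the stated order of events and should be fixed. The protocol ties the consent form to an arm fixed before consent, completed screening and baseline, and states no concealment. Refusal, and to a lesser degree judgement-based screening, can therefore differ between exercise, mindfulness and Cogmed.

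Confidence is high for the order and the arm-linked form, and moderate that a bias of consequence would follow. The range of 5.1% to 13.9% false positives is not a forecast: it depends wholly on the assumed refusal fractions, correlations, equal arms and pairwise tests. A reader might also infer that the trial is already biased, or that losses are replaced so as to hide imbalance. The protocol says neither; it permits the first and is silent on the second. Baselines taken with the arm possibly known are an added weakness of unknown direction.

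**What to change.** Use one consent form describing all four programs, with the two Cogmed programs in the neutral terms of the phone screen, so that the form does not show which is the control. Release a concealed assignment only after consent, confirmed eligibility and completion of Sessions 1 and 2, and before the home introduction visit.

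For anyone already assigned under the current order, report by arm everyone assigned, including those who declined or failed screening. Under the new order nobody can decline consent or fail screening by arm, so report everyone randomized by arm.

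The cost is an amendment to the consent form and procedures, with no added visits and no change in sample size. The existing accelerometer week between Session 2 and training leaves time to prepare the home visit, though at shorter notice than now. Confirming eligibility first may mean waiting for the mailed informant form. The change does not alter what subjects know at post-test.

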## Study Procedures

### Pre-Intervention Assessment

The initial screening evaluation will take place over two half-day sessions, each lasting 3 to 3.5 hours in a designated room in the Laboratory of Healthy Cognitive Aging, Center for Brain/Mind Medicine, BWH, [name].

The sessions can be completed over one or two days, depending on the subject’s preference.

### Pre-Intervention Assessment Session 1

The first session will include completion of informed consent, a medical history, demographic information, including socioeconomic status (SES), survey questionnaires, and tests of visual acuity.

### Screening Evaluation (for inclusion/exclusion)

#### Cognitive Screen

- *The Mini-Mental State Examination (MMSE)*, a broad cognitive test on memory, spatial ability, memory and orientation, commonly used to screen for cognitive impairment [87]
- *American National Adult Reading Test (AmNART)*, a test of word pronunciation that provides an estimated IQ [88]
- Logical Memory I and II, Wechsler Memory Scale—Third Edition, a test of verbal memory [91]
- *Boston Naming Test (Short-form, 15-items)*, a test of confrontation naming [89, 90].

#### Depression Screen

*Geriatric Depression Scale* [93]

#### Neurological/Physical Evaluation

Subjects will undergo a structured neurological examination. Height and weight will be obtained to calculate BMI. Visual acuity will be measured (Snellen wall chart).

#### Gait

Gait will be assessed through a procedure in which subjects walk 10 meters under two conditions:

## Detailed Protocol: SAGE

1. Single task (walking at a comfortable pace)
2. Dual task (walking at a comfortable pace while simultaneously counting backwards by 3's, beginning with a 3 digit number told to the subject)

Every trial involving serial 3's will start from a different three digit number to reduce learning effects. Subjects will be given an opportunity to carry out an untimed practice trial. Under the dual task condition, subjects will be instructed to perform as well as they can on both tasks (i.e., no specified prioritization). Each condition will be done 2 times, with the order counterbalanced across subjects. The first and last meter (gait start up and slow down) will not be counted in the measurements. Time to walk 8 meters and number of steps taken will be measured. Under the dual task, we will also track how many numbers are generated while carrying out the serial 3's task (both correct and incorrect responses). In addition, the single task of counting backwards by 3's for 20 seconds will be tested twice in a seated position (once prior to and once after the gait testing).

### Informant Questionnaire

Subjects will select someone who knows them well (family member or friend) to complete a set of questionnaires. One questionnaire will provide information about a person's level of functioning (based on the Clinical Dementia Rating Scale [94]), and another will inquire about a person's level of engagement (Apathy Scale [95]). The questionnaires will be enclosed with a letter explaining how to complete the forms. We will provide a stamped, addressed envelope to return the questionnaires to us. A backup plan will be to mail these materials directly to the informant selected. This would occur if the materials were misplaced or if the subject requests us to do so. Informants will be compensated for their time by a \$10 check that will be mailed to them.

### Outcome Measures (Dependent variables measured at baseline and after the 5 week intervention)

- *Cambridge Neuropsychological Test Automated Battery (CANTAB)*, a computerized assessment of cognitive functions:
  - CANTAB Paired Associate Learning (PAL) – assesses visual memory and new learning
  - CANTAB Attention Switching Task (AST) – measures cued attentional set-shifting
  - CANTAB Reaction Time (RTI) – measures speed of response to visual target when the stimulus is either predictable (simple RT) or unpredictable (choice RT)
  - CANTAB Spatial Span (SSP) – assesses working memory
  - CANTAB One Touch Stockings of Cambridge (OTS) – a test of non-verbal reasoning
- *Trail Making Test, Parts A and B*, tests of visual attention and task switching [96]
- *Digit Symbol Coding, WAIS-IV*, a test of processing speed [96]
- *Controlled Oral Word Association Test (COWAT)*, a test of verbal retrieval and word generation [97]
- *Categorical Fluency* (a test of rapid retrieval of semantic knowledge) [97]

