#### Post-Intervention Assessment

Shortly after completing their 5 week intervention program, subjects will return to our BWH Lab at [name] for 2 half-day sessions. Every effort will be made to have the subjects return to the Lab within 2 days of completing the training program.

During these sessions, we will repeat the following measurements, as described in the section on pre-intervention assessment:

Collection of blood

Cognitive Testing (CANTAB subtests, *Trail Making Test*, Parts A and B, *Digit Symbol Coding*, *WAIS-IV*, *Controlled Oral Word Association Test (COWAT)*) [96, 97]

Completion of questionnaires

Neurologic/gait assessment

ERP studies

Transcranial doppler studies

Subjects will be paid for their time, as follows:

Pre-intervention evaluation session 1	\$60
Pre-intervention evaluation session 2	\$60
Structured intervention	\$30/week for 5 weeks
Post-intervention evaluation session 1	\$60
Post-intervention evaluation session 2	\$60
Completion of all study components	\$60

Subjects who choose to discontinue participation will be paid for their time in a prorated manner. Check request forms will be sent to BWH (accounts payable) and a check will be mailed to the address designated by the subject. During the evaluation session, the cost of parking will be covered by a voucher applicable to any BWH parking facility.

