#### **Biostatistical Analysis**

## Detailed Protocol: SAGE

We will mainly use MANCOVA methods to compare the different conditions while controlling for various background factors, such as age and baseline cognitive performance. Cognitive change scores will be the main outcome variables. In addition, we will analyze changes from baseline in BDNF levels, gait score neural activity, as measured by ERPs, and degree of vascular coupling, as measured by TCDs.

In separate analyses, we will investigate whether various cognitive domains (e.g., executive functions, memory) are differentially affected by different types of stimulation. We will also perform separate analyses for closer investigation of how age, education, intelligence and mood may modify the experimental effects.

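### Categorical Fluency is declared a before-and-after outcome, but the list of cognitive tests to repeat after training leaves it out

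*Protocol*

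**What the plan says.** Three places in the protocol bear on this.

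- **Outcome Measures.** The heading sets the timing for everything beneath it: "Dependent variables measured at baseline and after the 5 week intervention". Five top-level entries follow: the CANTAB (with five subtests), Trail Making A and B, Digit Symbol Coding, COWAT and Categorical Fluency. The last two are separate entries with separate descriptions. COWAT is "a test of verbal retrieval and word generation" and Categorical Fluency is "a test of rapid retrieval of semantic knowledge".
- **Post-Intervention Assessment.** For the visits after training the protocol says "we will repeat the following measurements, as described in the section on pre-intervention assessment" and then gives a list. Its cognitive line reads "Cognitive Testing (CANTAB subtests, *Trail Making Test*, Parts A and B, *Digit Symbol Coding*, *WAIS-IV*, *Controlled Oral Word Association Test (COWAT", after which the brackets close and two literature citations follow. Categorical Fluency does not appear.
- **Biostatistical Analysis.** "Cognitive change scores will be the main outcome variables".

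No other section schedules Categorical Fluency after the intervention.

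**The concern.** A change score needs a value at both time points. One section promises both for Categorical Fluency. The section that tells staff what to do at the second visit provides only for the other tests. A coordinator who builds the visit checklist from the Post-Intervention Assessment section would not give the test, and a declared component of the main outcome would exist at baseline only.

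An analysis plan cannot repair this, because a value that was not collected shortly after the five weeks of training cannot be obtained later. The protocol also plans separate analyses by cognitive domain, and Categorical Fluency is the only entry described as testing semantic knowledge.

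There is a further, conditional risk. The trial plans 100 subjects at each of two sites. If the sites resolved the two lists differently, the test could lack a second value for 100 of 200 subjects. A multivariate analysis would then have to drop the variable or, under complete-case handling, drop those subjects. Nothing in the protocol says that this will happen.

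**Working it through.** No sample size, power or error rate is involved. The check is an item-by-item comparison of the two lists.

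| Top-level entry in Outcome Measures | Named in Post-Intervention Assessment? |
|---|---|
| CANTAB (five subtests) | Yes, collectively as the CANTAB subtests |
| Trail Making A and B | Yes |
| Digit Symbol Coding (WAIS-IV) | Yes |
| COWAT | Yes |
| Categorical Fluency | No |

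**Count by entry.** 5 declared, 4 carried over, 5 − 4 = 1 missing. The share is 1/5 = 20%.

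**Count by individual test.** 5 CANTAB subtests + Trail Making + Digit Symbol Coding + COWAT + Categorical Fluency = 9, so the share is 1/9, about 11%. With Trail Making A and B counted separately it is 1/10 = 10%.

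**Range of the loss.** It is 0 tests if the Outcome Measures heading governs and 1 test if the post-intervention list governs.

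Four readings could remove the mismatch:

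1. *The post-intervention list is shorthand.* It does refer back to the pre-intervention section. That reference can, however, be read as saying how the listed measurements are done, without adding unlisted ones. The cognitive line names its tests and contains no wording to mark them as examples.
2. *COWAT is meant to include category fluency.* Outcome Measures gives the two tests separate entries and descriptions, so the protocol treats them as different tests.
3. *The citation shows that the test is included.* The cognitive line ends with references 96 and 97. Outcome Measures attaches reference 97 to COWAT as well as to Categorical Fluency, so its presence is explained by COWAT alone.
4. *Text was lost in conversion or redaction.* The brackets close and the citations follow in order. Nothing suggests a gap.

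None of the four settles the question.

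**The case against.** The strongest reply is that this is an incomplete list and not a conflict between two rules. The Outcome Measures heading states the timing explicitly for every test under it. The Post-Intervention Assessment section never says that Categorical Fluency is dropped or is baseline-only, and it points back to the section where the test is listed. Most of its other lines are bare labels for blood, questionnaires, ERP and Doppler studies, so staff must consult the earlier section anyway. Giving every declared test satisfies both passages.

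The effect is also limited. The other tests keep both time points. If the test were skipped uniformly it would be absent from all four arms alike, so the randomised comparison would not be biased. The analysis section gives Categorical Fluency no special role, and its example domains are executive functions and memory. Counted by individual test, the share is nearer one in nine than one in five.

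Much of this stands. The Outcome Measures reading is the more natural one, the omission is probably a slip, and the loss is conditional. What does not stand is that the text resolves itself. Cognitive testing is one of the few lines where the post-intervention list itemises its content, and a reader may reasonably take an itemised list as complete.

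**Conclusion.** The inconsistency is real and stands in the current text. Categorical Fluency is declared a before-and-after outcome but is missing from the only instruction that says which cognitive tests to repeat. It affects 1 of 5 outcome entries (1 of 9 individual tests). The resulting loss is between none and the whole change score for that test, depending on which section staff follow.

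The conclusion assumes only that the post-intervention list could be used as written to run the visit. It does not assume that the test was in fact omitted, and it does not call the trial's conclusions into question. The point should be corrected because both sections are operative data-collection text, the main outcome is built from change scores, and a missed second measurement is irrecoverable.

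**What to change.** Add Categorical Fluency to the cognitive testing line of the Post-Intervention Assessment section. This agrees with the timing already stated in the Outcome Measures heading. If the test was intended for baseline only, move it out of the before-and-after outcome list instead, so that no change score is expected from it. Either way, both sites should work from the same reconciled list.

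The cost is one line of text. If the test is added, there is also one brief test at a visit that already takes place, using a procedure that staff already carry out at baseline.
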